We propose a prospective, randomized, double-blinded, placebo-controlled clinical trial on the use of perioperative intravenous lidocaine infusion in order to decrease pain scores and opioid consumption after robotic-assisted prostatectomy and robot assisted partial nephrectomy.

Patients undergoing urological robotic assisted surgery will be randomized 1:1 to receive either intraoperative 0.8% lidocaine or normal saline at 1 mg/kg/h for patients younger than 65 years and 0.5 mg/kg/h for patients greater than or equal to the age of 65 to be delivered by continuous infusion for 24 hours intra- and post-operatively. Opioid use will be monitored for up to 14 days post-operatively as well as pain scores.

OBJECTIVES AND SCIENTIFIC AIMS

Clinical Hypotheses:

Primary Hypothesis:

We hypothesize that use of perioperative lidocaine infusion for 24 hours in urology robotic surgeries would result in less pain and less opioid use compared to the placebo.

Exploratory Hypotheses:

We hypothesize that the use of the lidocaine infusion compared to placebo would:

1. result in less opioid consumption in first 24 hours and 14 days post-operatively
2. decrease length of stay in the PACU and improve SpO₂ levels in PACU
3. decrease postoperative nausea and vomiting
4. decrease time to first ambulation after the surgery
5. improve recovery of bowel movements after surgery
6. improve patient satisfaction levels after surgery
7. decrease length of stay in hospital

Therefore:

Primary Endpoint is:

- Difference in post-operative pain

Secondary Endpoints are:

- Difference in opioid consumption in first 24 hours, discharge and 14 days post-operatively (utilizing morphine equivalents)
- Difference in length of hospital stay determined by surgeon excluding social factors that may delay discharge (discharge readiness; hours)
- Difference in post-operative ileus duration (hours)
- Difference in time in the Post Anesthesia Care Unit (PACU) after surgery (discharge readiness and actual discharge; minutes)
- Difference in return of flatus after surgery (hours)
- Difference in time to out of bed to chair after surgery (hours)
- Difference in time to first ambulation in the hallway after surgery (hours)

BACKGROUND AND STUDY DESIGN/INTERVENTION

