Lauwick et al.¹⁸ investigated functional walking capacity as a measure of recovery from a laparoscopic prostatectomy and discovered that patients who received lidocaine infusion were able to walk further over a shorter amount of time (56 vs. 43.5 meters) compared to saline. They received 1.5mg/kg bolus, 2mg/kg during the operation and 1mg/kg in the PACU for 24 hours after surgery. They also had 12% reduction (5.6 vs 6.3) of desflurane during the operation.

Groudine et al.¹⁹ demonstrated value of intravenous lidocaine in patients undergoing radical retropubic prostatectomy after infusing 1.5mg/kg bolus, followed by 1.5mg/kg/h infusion from beginning of surgery until 1 hour postoperatively. Patients had quicker return of flatulence, regained of bowel function faster (p<0.05), 1.1 fewer days in the hospital (p <0.05), and decreased postoperative pain¹⁹.

Jendoubi et al.¹⁴ looked at the use of intravenous lidocaine or ketamine compared to saline for acute and chronic pain following open nephrectomy. They gave 1.5 mg/kg bolus at anesthesia induction followed by infusion of 1 mg/kg/h intraoperatively and continued for 24 hours. They found that both ketamine and lidocaine significantly reduced morphine consumption by about

33% and 42%, respectively ($p<0.001$), improved 6-minute walk distance at discharge from a mean of 27 meters to 82.3 meters in the lidocaine group (0.001), and also reduced development of neuropathic pain at 3 months ($p<0.05$).

Tauzin-Fin et al.²⁹ found significant enhancement of recovery with several endpoints revealing reduction of morphine 8.5mg in lidocaine infusion vs 25mg control group, improved post-operative pain ($P<0.05$), time to first flatus ($P<0.001$) and 6-minute walk time ($p<0.001$) after a nephrectomy. Effective analgesia in the post-operative period considerably improves rehabilitation.

Weinberg et al.²⁰ looked at radical prostatectomy patients with perioperative lidocaine 2% or saline. A pre-operative intravenous bolus of 0.075mg/kg followed by peri-operative and 24-hour post-operative infusion of 0.075mg/kg/h. They found it decreased hospital stay an average of 1.3 days ($P=0.017$), reduced pain at rest by 1.8 hours ($p=0.001$), and morphine consumption by a mean of 13.9mg ($p=0.021$).

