This is a prospective, randomized, double-blinded, placebo-controlled clinical trial on lidocaine infusion for pain control and opioid consumption in patients undergoing either robotic-assisted laparoscopic prostatectomy or robotic-assisted laparoscopic partial nephrectomy at University of Missouri Hospital. Patients will be randomized in a 1:1 fashion and stratified by the type of surgery to receive a perioperative intravenous 0.8% lidocaine infusion at 1 mg/kg/h if $<$ age 65 and 0.5 mg/kg/h if \geq age 65 or an equal volume and rate of normal saline as a placebo. The infusion will be started 15 minutes after endotracheal intubation and continue for 24 hours.

After obtaining written consent, subjects will be randomized to receive lidocaine or normal saline. The anesthesiologist, surgeon, nurses, research staff, and patient will be blinded to the intervention. Masked infusion bags of 0.8% lidocaine or normal saline will be prepared by the investigational pharmacy at University of Missouri Hospital. To avoid any compromise in the blinding process, the investigational pharmacist will enter "Study Medication" in the medical record.

Perioperative care, surgery and anesthesia, for all subjects will be per standard hospital protocol.

In short:

Upon arrival to the operating room, patients will be placed supine on the operating table and intravenous (IV) lines connected to allow initiation of IV lidocaine or saline following anesthetic induction. IV antibiotics will be utilized if clinical necessary based on the discretion of the anesthesiologist and attending surgeon. Standard perioperative monitoring including a

continuous electrocardiogram, pulse oximetry, urine output, non-invasive arterial pressure measurement, end-tidal CO₂ and temperature will be utilized. Intravenous fluid use during surgery will be provided by the anesthesiology team as clinically indicated. Anesthesia will be standardized. Induction will be with lidocaine 1.5 mg/kg, fentanyl 1 mcg/kg, propofol 1.5 to 2 mg/kg, and rocuronium 0.6 mg/kg. Patient will then be prepared and draped in sterile fashion. Timeout will be performed.

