Patient may go to the floor or ICU with the infusion. Orders will be included in surgeon's post-operative orders including the stop time at 24 hours. The infusion pump will be programmed using Guardrails settings, it will be on separate infusion pump from IV fluids with sign for pump - local toxicity, obtained from anesthesia pain nurse.

Patients will be monitored clinically for toxicities during the postoperative period. Per standard of care the nurse caring for the patient will be required to document any adverse events to lidocaine every four hours and anesthesiology pain nurses will monitor these reports. If patients experience the presence of perioral paresthesia, metallic taste, tinnitus, confusion, agitation,

muscle spasms, and seizures, the lidocaine infusion will be stopped and a lidocaine toxicity protocol will start by the standard of care. The subject will be removed from the study.

At initial follow-up appointment, patient will be asked to bring in prescribed opioids, if applicable, to determine how much was required in their outpatient recovery. Pill count will be done and compared to distributed quantity. VAS score will be also assessed.

THERAPEUTIC AND DIAGNOSTIC AGENTS

Lidocaine is the intravenous analgesic. Lidocaine infusion will be stored and dispensed by the Investigational Pharmacy at University Hospital. A 0.8% Lidocaine infusion will be injected intravenously using an administration set with a filter at a constant rate of 1 mg/kg/h for ages < 65 and 0.5 mg/kg/h for ages ≥ 65. Patients with BMI ≥ 40 will be dosed using ideal body weight.

RECRUITMENT PLAN

Patients will be recruited from the practices of the Division of Urology, Department of Surgery. The study will be introduced to every eligible patient scheduled for robot assisted laparoscopic prostatectomy and robot assisted laparoscopic partial nephrectomy by the participating consenting physicians from the Department of Surgery-Urology Division and a written consent obtained prior to surgery by the consenting research personnel. Candidate subjects will be provided time to consider the study, to read the informed consent document at their convenience, and discuss the study with family and others, as desired.

PRETREATMENT EVALUATION

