Various symptoms including perioral paresthesia, metallic taste, tinnitus, confusion, agitation, muscle spasms, and seizures have been described when the plasma lidocaine was higher than 5 $\mu\text{g}/\text{mL}$. While under general anesthesia, evidence of toxicity may be evident through bradycardia, increased intervals and widening QRS complex and may be increased with hypercapnia.¹⁶ However, it has been shown to be more cardio-protective, rather than cardio-toxic in prospective randomized study³⁶. The toxic levels of lidocaine are unlikely to be experienced at the levels used in our protocol. Our study is using the low end of the recommended dose and rate of 1-2 mg/kg/h. We additionally are utilizing a bolus only as a part of routine anesthesia induction, which is recommended to be 1-2 mg/kg and start the infusion 15 minutes after the endotracheal intubation.

Signs of lidocaine toxicity will be monitored per University Hospital standard of care protocol. This includes assessment and documentation by floor nursing staff, every 4 hours, of the signs and symptoms of lidocaine toxicity. The presence or lack of toxicity is reported in the medical record at these time points and pain nurse with the Department of Anesthesiology and Perioperative Medicine review this information. Management and review of medications will also be performed by the surgical and inpatient care teams per standard of care. Toxicity in our study will be evaluated clinically postoperatively by the presence of perioral paresthesia, metallic taste, tinnitus, confusion, agitation, muscle spasms, and seizures. Following standard of care, if there is concern of possible toxicity a lidocaine level may be ordered per standard of care.

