Two statistical analysis methods will be used to make a comparison between the two treatment groups with regard to the primary end point: (i) to assess the difference of pain level between the two groups at specific time point, Wilcoxon Rank Sum Test will be used, (ii) to assess the pattern of change in pain level over the study period between the two groups, a Generalized Estimation Equation (GEE) model will be used.

Sample Size					Drop-out Inflated Enrollment	
Treatment	Placebo	Effect Size	SD	Power	Treatment	Placebo
20	20	2	2	80%	23	23
27	27	2	2	90%	30	30

*A dropout rate of 10% was considered here. A Two Sample T-test using effect size sample size method was used to get an estimate of the samples needed from the PASS program.

Table 2: Sample size assuming 80% and 90% power.

RESEARCH PARTICIPANT REGISTRATION AND RANDOMIZATION PROCEDURES

Research Participant Registration

Confirm eligibility as defined in the section entitled Criteria for Patient/Subject Eligibility.

Obtain informed consent, by following procedures defined in section entitled Informed Consent Procedures.

Randomization

Randomization will be accomplished by the method of random permuted block and stratified by the type of the surgery and subject age. Since this is a double-blind study, the subjects' treatment assignments will be kept in a blinded randomization table. The Excel column containing treatment designation assigned by a biostatistician will be occluded from view to maintain blinding. The investigational pharmacist will not be blinded and will have the randomization table. After recruitment, research staff will randomize the patient into the correct stratification and the Investigation Pharmacy will be notified. If it is clinically necessary to unblind a subjects' treatment allocation this will be done using the randomization table.

DATA MANAGEMENT ISSUES

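### The toxicity section places the regimen at the low end of 1-2 mg/kg/h, but patients aged 65 or over receive 0.5 mg/kg/h, and no estimate by dose tier is planned, so a null pooled result could not be told from a diluted one

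*Combined protocol and SAP*

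**What the plan says.** Toxicities/Side Effects describes the whole study in one sentence: "Our study is using the low end of the recommended dose and rate of 1-2 mg/kg/h". It follows directly on the safety statement "The toxic levels of lidocaine are unlikely to be experienced at the levels used in our protocol".

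The dosing statements differ from that description. The opening summary gives "1 mg/kg/h for patients younger than 65 years and 0.5 mg/kg/h for patients greater than or equal to the age of 65", and Therapeutic and Diagnostic Agents gives the infusion "at a constant rate of 1 mg/kg/h for ages < 65 and 0.5 mg/kg/h for ages ≥ 65". Design and Intervention repeat the same two rates. No section explains the lower rate or relates it to the 1-2 mg/kg/h range.

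There is one primary hypothesis for all patients, that "use of perioperative lidocaine infusion for 24 hours in urology robotic surgeries would result in less pain and less opioid use". Under Biostatistics, the sample size assumes a single 2-point difference with SD 2. The unadjusted two-group comparison is primary. The adjusted analysis names only type of surgery as an example covariate. Proposed Analyses adds a Wilcoxon test at a specific time point and a GEE model over time, neither by age or dose tier.

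The Randomization section says allocation is "stratified by the type of the surgery and subject age", without an age cut-point. Design and Surgical Intervention Plan mention stratification by type of surgery only.

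**The concern.** A stated property of the regimen is wrong for an entire dose tier. A reader of the toxicity section alone would conclude that every patient in the lidocaine arm is infused at 1 mg/kg/h or slightly more.

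The infusion is also the whole contrast between arms. Induction lidocaine belongs to the standardised anaesthetic for all subjects ("Induction will be with lidocaine 1.5 mg/kg, fentanyl 1 mcg/kg"), so from age 65 the difference between arms, per kg and per hour, is half what it is below 65. The power calculation and the primary test treat that contrast as uniform.

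If the lower rate works less well, the pooled difference is smaller than planned. With no pre-specified tier estimate, a null result leaves two explanations open: lidocaine does not help, or its effect was diluted. Tier estimates produced after seeing the data would carry much less weight.

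**Working it through.** **1. The rates side by side.** Stated range: 1-2 mg/kg/h. Rate below age 65: 1 mg/kg/h, at the lower limit. Rate from age 65: 0.5 mg/kg/h, and 0.5 / 1 = 50% of the lower limit. The four dosing statements agree with each other; only the toxicity sentence departs from them.

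**2. The cited rates.** Every rate per kg in Table 1 is at least 1 mg/kg/h. The two in µg/kg/min convert as 30 × 60 / 1000 = 1.8 and 33 × 60 / 1000 = 1.98 mg/kg/h. Lower figures do appear, however. Table 1 has fixed rates that go down to 1 mg/min (a colorectal and a cardiac study). That is 60 mg/h, which is below 1 mg/kg/h for anyone over 60 kg (0.75 mg/kg/h at an assumed 80 kg). The background also reports benefit in a prostatectomy trial with a printed "24-hour post-operative infusion of 0.075mg/kg/h". The cited evidence is therefore mostly, not wholly, at 1 mg/kg/h or more.

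**3. The plan's own sample size.** Inputs from Biostatistics: difference 2, SD 2, two-sided 5%. The exact t-test needs 17 per arm for 80% power and 23 for 90%. Dividing by 0.864, the minimum asymptotic relative efficiency of the Wilcoxon test, gives 17 / 0.864 = 19.7, so 20, and 23 / 0.864 = 26.6, so 27. With 10% dropout, 20 / 0.9 = 22.2, so 23, and 27 / 0.9 = 30. All match Table 2. Simulated Wilcoxon power at 20 per arm, with normal data and a uniform 2-point effect, is about 84-85%.

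**4. Dilution.** Two inputs are not in the documents and are assumed: the share *p* aged 65 or over (30-60%), and the ratio *r* of the effect at 0.5 mg/kg/h to the 2-point effect.

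Pooled difference = 2(1 − p) + 2rp.

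For p = 0.5 and r = 0.5 this is 1 + 0.5 = 1.5 points. Simulated Wilcoxon power at 20 per arm (SD 2, same share in both arms, 20,000 runs):

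| Share ≥65 | r = 1 | r = 0.75 | r = 0.5 | r = 0 |
|---|---|---|---|---|
| 30% | 85% | 79% | 71% | 52% |
| 40% | 85% | 77% | 66% | 39% |
| 50% | 85% | 74% | 60% | 27% |
| 60% | 85% | 72% | 54% | 19% |

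A separate set of 4,000 runs gave 72% to 54% for r = 0.5 and 51% to 19% for r = 0, which agrees within about one point.

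**5. What tier estimates could show.** Assume an even split, 10 per arm per tier.
- SE of the difference in one tier: 2 × √(2/10) = 0.894. 95% CI half-width: 2.101 × 0.894 = 1.88, about ±1.9 points.
- SE of the difference between tiers: √2 × 0.894 = 1.265.
- Power of the treatment-by-tier test (36 df): about 12% if the effect is halved at the lower rate (tiers differ by 1 point), and about 34% if it is absent (tiers differ by 2 points).

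**The case against.** The strongest reply is that the age-tiered rate is the intervention. It is stated consistently in four places, and the trial compares that regimen with placebo. This stands. Randomisation protects the comparison of arms whatever the mix of ages, and stratification by age would add balance. A reader might infer that a null result would fail to test the regimen the plan justifies. The documents do not support that: patients under 65 receive 1 mg/kg/h, and the pooled comparison is valid for the regimen as defined. A null result would be ambiguous, not a non-test.

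The sentence at issue also argues safety, and a rate below the range does not weaken a safety argument. That stands too, but the sentence still misdescribes the regimen.

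Three other stronger readings fail:
- That the cited evidence covers only the younger tier. This confuses dose rate with patient age. The documents give no age distribution for the cited trials, and lower rates are cited (working, step 2), although the Table 1 rows do not isolate benefit at 1 mg/min.
- That two different exposures are being mixed. The documents show two dose rates. They give no plasma levels by age, and a level is ordered only if toxicity is suspected.
- That power is certainly lost. If the lower rate works equally well, nothing is lost.

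Finally, tier estimates from this sample cannot resolve the ambiguity. That is correct, and it limits what the remedy may be used for.

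**Conclusion.** The point holds in a limited form. The toxicity section's description is contradicted by every dosing statement for patients aged 65 or over, and the passages must be reconciled. The primary analysis applies one assumed difference to two dose rates, and no estimate by tier is planned, although age sets the rate and the Randomization section lists it as a stratum.

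The consequence is for interpretation and possibly power, not bias. Its size cannot be fixed from the documents. Over an assumed 30-60% share aged 65 or over, it runs from no loss (about 84-85% power) through about 72-54% to about 51-19%, depending on whether the lower rate has the full effect, half of it or none. These figures assume normal data with SD 2 and equal shares in both arms. The change is worth making because it is cheap and is credible only if specified in advance.

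**What to change.** 1. Reconcile the toxicity sentence with the dosing statements so that all sections describe the same regimen. No view is taken here on which rate is right.
2. State in Randomization that the age stratum is cut at the age that sets the infusion rate, and align Design and Surgical Intervention Plan with it.
3. State that the pooled primary result estimates the effect of the age-tiered regimen against placebo.
4. Name age tier, with type of surgery, as a covariate in the adjusted analysis.
5. Pre-specify the treatment difference with a 95% CI in each age tier, plus a treatment-by-tier term, labelled descriptive.

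The cost is wording and a few extra estimates from data already collected; no more patients are needed. The downside is imprecision: about ±1.9 points per tier, and 12-34% power for the interaction in the scenarios above. For that reason the tier estimates must not decide how the pooled result is read, and a non-significant interaction must not be taken as evidence that the two rates work equally well.

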Anesthesia will be maintained with 1 MAC sevoflurane, additional fentanyl and rocuronium will be given per anesthesia discretion. Quantity of all anesthetic and analgesic medications during the operation will be documented. Local 0.25% bupivacaine (10mL) without epinephrine injection will be used post-operatively during closure in all patients regardless of being in the study group or control group as a part of normal operational procedure. Reversal of neuromuscular blockade will be with sugammadex 2 mg/kg. When standard extubation criteria are met the subject will be extubated and transported to PACU.

Intervention

Fifteen minutes following endotracheal intubation, subjects will be intravenously infused with either 0.8% lidocaine at 1 mg/kg/h if < age 65 and 0.5 mg/kg/h if ≥ age 65 or an equal volume and rate of normal saline placebo as determined by the randomization table. The infusion will be continued for 24 hours after surgery. Masked infusion bags of 0.8% lidocaine or normal saline will be prepared by the Investigational Pharmacy at the University of Missouri Hospital according to the subject randomization table. Infusion preparation will occur in a blinded fashion to all clinical and research personal involved with the study case. To maintain blinding, the investigational pharmacist will enter "Study Medication" in the medical record.

In PACU patient will receive additional fentanyl or hydromorphone. Postoperative pain scores, vital measures, and opioid use will be documented. Once patient is able to tolerate oral intake, they will be switched to oral narcotics. Patient fentanyl consumption and 10 cm visual analog scale (VAS) will be utilized. VAS will be scored from a 0 "no pain" to a 10 "worst pain ever" and will be recorded by blinded research staff at 1, 2, 4, 6, 12, 24 hours post-operatively, postop day 2, any additional day during hospitalization, at time of discharge and 14-day follow up. The nurse that will be caring for these patients will document the time of first bowel movement, return of flatus and any adverse reactions per standard of care. Post-Anesthesia Patient Satisfaction Assessment will be performed at 24 h post-surgery.

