Length of hospital stay will be defined as the time the subject leaves the OR until subject meets standardized discharge criteria according to the surgeons' protocol, which will exclude social factors delaying real discharge times.

Post-operative ileus duration is defined as return of bowel function in hours from extubation per patients recall following nursing inquiry. Documentation will be done per standard of care by the nurse caring for study patient.

Flatus return is defined as return of flatus in hours from extubation per patients recall following nursing inquiry. Documentation will be done by nurse caring for patient following standard of care.

Patient satisfaction will be assessed 24 hours post-operative by Post Anesthesia Patient Satisfaction Assessment by research staff.

CRITERIA FOR REMOVAL FROM STUDY

Patients will be withdrawn from the study if they express a desire to do so, if it is determined to be in the patient's best interest to do so, or if they do not undergo initiation of their surgical procedure as stipulated previously. If lidocaine infusion is stopped subject will be excluded from analysis. If surgery is converted from robotic assisted to open the subject will be excluded from analysis. Patients who are not evaluable for the study primary endpoint by failure to obtain

data for the primary endpoint will be excluded from the study and further analysis will not be performed.

BIOSTATISTICS

Sample Size

The primary outcome for the study is the patient's pain score at discharge. Although additional analyses are planned, the sample size estimate is based on this outcome. Assuming a common standard deviation of two-points, a sample size of 40 with 20 per treatment arm will provide 80% power to detect a 2-point difference between groups when testing a two-sided alternative at the 5% level of significance using Wilcoxon Rank Sum Test. To take into account the loss to follow up, the drop-out inflated enrollment will be 46 subject with 23 subjects in each group assuming the same power.

Unadjusted and Adjusted Analysis

The unadjusted analysis will be designated as primary analysis and it will be performed to assess the pain level difference between the two groups. The adjusted analysis which will be designated as secondary analysis will incorporate other covariates like type of surgery in addition to the treatment assignments as covariate.

Proposed Analyses

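### Flatus and bowel-function times are collected only by bedside inquiry, so comparing recorded hours could favour an arm that goes home sooner; the size is unknown and the risk lies mainly with first bowel movement

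*Combined protocol and SAP*

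**What the plan says.** **Definitions** (Criteria for Therapeutic Response/Outcome Assessment). For ileus: "Post-operative ileus duration is defined as return of bowel function in hours from extubation per patients recall following nursing inquiry". The next sentence adds: "Documentation will be done per standard of care by the nurse caring for study patient". For flatus: "Flatus return is defined as return of flatus in hours from extubation per patients recall following nursing inquiry".

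**Collection** (Intervention). The nurse caring for the patient is to "document the time of first bowel movement, return of flatus and any adverse reactions per standard of care".

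**Follow-up visit** (end of Intervention). Two items are listed. For opioids, the "patient will be asked to bring in prescribed opioids, if applicable, to determine how much was required in their outpatient recovery". For pain, "VAS score will be also assessed". Flatus and bowel movement are not mentioned, and no diary or telephone call is planned.

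**Endpoints and hypothesis** (Objectives and Scientific Aims). Both times are secondary endpoints, expressed as a between-arm difference in hours. The exploratory hypotheses include that lidocaine will "decrease length of stay in hospital".

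**Analysis** (Biostatistics, Proposed Analyses). The two methods named, Wilcoxon rank sum and GEE, are for the primary endpoint. No method is given for flatus or bowel function, and no rule covers a patient discharged before the event.

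**The concern.** A time gathered by bedside inquiry exists only if the event happens while someone is still asking. A patient who goes home first has no value, and the lost values are the late ones. With the same observation window in both arms the loss is balanced. With a shorter window on lidocaine, more late times are lost there, and the recorded hours look shorter than on placebo.

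The trial itself anticipates a shorter window. Besides the hypothesis, its Background cites two prostatectomy trials with stays 1.1 and 1.3 days shorter on lidocaine. It also cites one laparoscopic renal trial with no significant difference in stay.

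At stake is the reading of two secondary endpoints. Better bowel recovery is a stated hypothesis, so a favourable difference would be read as benefit. If many patients left before the event, it could not be told apart from earlier discharge.

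**Working it through.** The plan states no figure for these endpoints, so there is none to reproduce. The sample size concerns pain at discharge and is not touched.

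**Inputs.** From the documents: the source of the times, the content of the follow-up visit, the hypothesis of shorter stay, a 24-hour infusion and 20 analysed patients per arm. Assumed, because the documents are silent: event medians, discharge times, their spread, and discharge unrelated to bowel recovery. 'Return of bowel function' is taken to mean first bowel movement; the documents do not equate the two.

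**Model 1: size of the bias with no true effect.** Event time T is Weibull with shape 1.5 and median m, the same in both arms, so S(t) = 2^(−(t/m)^1.5). Discharge D is normal with SD 10 h, not earlier than 24 h.

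- Share with no value = E[S(D)].
- Recorded mean = ∫ t f(t) P(D ≥ t) dt ÷ ∫ f(t) P(D ≥ t) dt.

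Hand check with discharge fixed at its mean and m = 36 h. Lidocaine leaving at 36 h: 2^(−1) = 0.50 without a value. Placebo leaving at 48 h: (48/36)^1.5 = 1.54 and 2^(−1.54) = 0.34. With the spread in D, numerical integration gives (placebo v lidocaine):

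| Event median (h) | Mean discharge (h) | No value | Recorded mean (h) | False difference (h) |
|---|---|---|---|---|
| 36 | 48 v 48 | 36% v 36% | 25.4 v 25.4 | 0 |
| 8 | 48 v 36 | 0.1% v 0.6% | 9.2 v 9.1 | −0.1 |
| 12 | 48 v 36 | 1.2% v 4.6% | 13.5 v 12.8 | −0.7 |
| 24 | 48 v 36 | 16% v 29% | 21.9 v 18.6 | −3.3 |
| 36 | 32 v 28 | 55% v 59% | 19.2 v 17.7 | −1.5 |
| 36 | 48 v 42 | 36% v 43% | 25.4 v 23.1 | −2.3 |
| 36 | 48 v 36 | 36% v 50% | 25.4 v 20.8 | −4.6 |
| 48 | 48 v 36 | 51% v 63% | 27.1 v 21.8 | −5.3 |
| 60 | 48 v 36 | 61% v 72% | 28.1 v 22.4 | −5.7 |

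**Model 2: false-positive rate at the trial's size.** Lognormal event and discharge times (log-SD 0.5 and 0.25), 20 per arm, 4,000 runs, no true effect. The Wilcoxon test uses recorded values only; the log-rank test censors at discharge.

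| Event median (h) | Median discharge, placebo v lidocaine (h) | Have a value | False difference (h) | Wilcoxon error | Log-rank error |
|---|---|---|---|---|---|
| 12 | 48 v 36 | 99% v 98% | −0.3 | 4.9% | 5.3% |
| 30 | 36 v 36 | 63% v 63% | 0 | 4.5% | 5.8% |
| 30 | 48 v 36 | 80% v 63% | −3.3 | 11.4% | 5.1% |
| 48 | 48 v 36 | 50% v 30% | −5.5 | 11.7% | 5.4% |

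When discharge was given a correlation of 0.5 with bowel recovery (medians 30 and 48 h, discharge 48 v 36 h), the log-rank error was 5.8% and 6.5%. The Wilcoxon error was 11.6% and 13.7%.

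The two models agree on direction. The bias needs both discharge before the event and unequal stays; without either it is negligible.

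**The case against.** **The discharge criteria are not shown.** Length of stay ends when the patient meets criteria in the surgeons' protocol, which is not reproduced. If these require flatus, or bowel function, few or no such times are lost. This stands, and it makes the point conditional.

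**Flatus may be unaffected.** A reader might infer that both endpoints are equally at risk. The documents do not support that: they give no median for either event, and at assumed medians of 8 to 12 h the bias is 0.1 to 0.7 h. The case is mainly about first bowel movement.

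**The plan does not say it will drop missing times.** A reader might infer that recorded means will be compared. In fact no analysis is stated, and a difference in hours could be a difference in Kaplan-Meier medians. This stands as far as analysis goes. It does not remove the collection gap: a time never asked for cannot be recovered by any method.

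**Only inpatient collection is an inference.** The plan never says so outright. It follows from two statements naming the nurse and from a follow-up list without bowel function. The observation window also ends at actual discharge, whereas the stay endpoint uses readiness, so social delays would lengthen the window.

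**A false claim of benefit is not the likely result.** With stays 12 h apart, the Wilcoxon error in Model 2 is about 12% or less when discharge is unrelated to bowel recovery. An error of 34% appeared only with a 22 h difference in stay (48 v 26 h, event median 30 h).

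**Conclusion.** The point holds conditionally. As written, the plan collects both times only while the patient is in hospital and has no rule for an event after discharge. If some patients leave first and lidocaine patients leave sooner, recorded hours favour lidocaine with no bowel effect.

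The size cannot be fixed from the documents. Under the assumptions shown it runs from about 0 h (equal stays, medians of 8 to 12 h, or discharge that requires the event) to about 5 to 6 h (first bowel movement median 36 to 60 h, stay 12 h shorter). The upper figures rest on discharge being unrelated to bowel recovery and on recorded values alone being compared.

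The documents do not support reading this as a demonstrated bias, as a problem shown for flatus, or as a threat to the primary endpoint or the sample size. It is a gap in two secondary endpoints that should be closed because closing it is cheap.

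**What to change.** 1. **At discharge:** for each patient with no flatus or no bowel movement, record that status and the time of the last inquiry. State whether return of bowel function means first bowel movement.
2. **At the follow-up visit already planned:** ask these patients for the date and approximate time of the event.
3. **Analysis text:** analyse both endpoints as time from extubation to event, with Kaplan-Meier estimates and a log-rank test, in all patients retained in the analysis. This cannot mean every randomised patient while the plan excludes stopped infusions, conversions to open surgery and patients without primary-endpoint data. Treat home events recalled later as interval-censored, using a version of the methods that allows for it. Censor at last inquiry only when nothing later is obtained.
4. **Reporting:** give the share without an event at discharge by arm, and note that censoring at discharge may be informative if leaving depends on bowel recovery.

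**Cost:** one extra question at an existing visit, one discharge field and a short analysis paragraph. The downside is imprecise recall at 14 ± 7 days, which is why these times should enter as intervals. No treatment or clinical rule changes.
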